10.5.3. Reporting Standards for Pharmacokinetic

Pharmacokinetic Concentration Data	
PC Windows Non-Linear (WNL) File	WNL file will be produced for PK parameters. Note: Concentration values will be imputed as per GUI_51487
Descriptive Summary Statistics, Graphical Displays and Listings	Refer to IDSL PK Display Standards. Refer to IDSL Statistical Principle 6.06.1. Note: Concentration values will be imputed as per GUI_51487 for descriptive summary statistics/analysis and summarized graphical displays only.
NONMEM/Pop PK File	Pop-PK file (CSV format) for the POP-PK analysis by Clinical Pharmacology Modelling and Simulation function will be created according to the data specification detailed in Section 9.1 Data Specification of the Pop-PK RAP (RAP-IVF116828-201558-205920-PopPK, located in Cabinets/Study File/GR121619/_Project/Meta Analysis/ RAP-IVF116828-201558-205920-PopPK)
Pharmacokinetic Parameter Derivation	
PK Parameter to be Derived by Programmer	The following PK parameters will be derived by the Programmer: Cp10, Cp20 and Cp30

10.6. Appendix 6: Derived and Transformed Data

10.6.1. General

Multiple Measurements at One Analysis Time Point

 • Mean of the measurements will be calculated and used in any derivation of summary statistics but if listed, all data will be presented. • Participants having both High and Low values for Normal Ranges at any post-baseline visit for safety parameters will be counted in both the High and Low categories of “Any visit post-baseline” row of related summary tables. This will also be applicable to relevant Potential Clinical Importance summary tables.
Study Day

 • Calculated as the number of days from First Dose Date: 
 • Ref Date = Missing → Study Day = Missing • Ref Date < First Dose Date → Study Day = Ref Date – First Dose Date • Ref Date ≥ First Dose Date → Study Day = Ref Date – (First Dose Date) + 1

10.6.2. Study Population

Demographics
Age

 • GSK standard IDSL algorithms will be used for calculating age. • Randomization date will be used as reference date to calculate age
Body Mass Index (BMI)

 • Calculated as Weight (kg) / [Height (m)²
Extent of Exposure

 • Number of days of exposure to study drug will be calculated based on the formula: Duration of Exposure in Days = Treatment Stop Date – (Treatment Start Date) + 1 • Participants who were randomized but did not report a treatment start date will be categorised as having zero days of exposure. If there are any treatment breaks during the study, exposure data will be adjusted accordingly.

10.6.3 Safety

ECG Parameters
RR Interval

 IF RR interval (msec) is not provided directly, then RR can be derived as : 
 [1] If QTcB is machine read & QTcF is not provided, then : $RR = [(QT/QTcB)^{(2)}] * 1000$ [2] If QTcF is machine read and QTcB is not provided, then: $RR = [(QT/QTcF)^{(3)}] * 1000$ If ECGs are manually read, the RR value preceding the measurement QT interval should be collected values THEN do not derive.
Corrected QT Intervals

 When not entered directly in the eCRF, corrected QT intervals using Bazett's (QTcB) and Fredericia's (QTcF) formulas will be calculated, in msec, depending on the availability of other measurements. IF RR interval (msec) is provided or calculated then missing QTcB and/or QTcF will be derived as : 
 $QTcB = \frac{QT}{\sqrt{\frac{RR}{1000}}}$ $QTcF = \frac{QT}{\sqrt[3]{\frac{RR}{1000}}}$ 

Laboratory Parameters

 If a laboratory value which is expected to have a numeric value for summary purposes, has a non-detectable level reported in the database, where the numeric value is missing, but typically a character value starting with '<x' or '>x' (or indicated as less than x or greater than x in the comment field) is present, the number of significant digits in the observed values will be used to determine how much to add or subtract in order to impute the corresponding numeric value. 
 ○ Example 1: 2 Decimal Points = '< x' becomes x - 0.01 ○ Example 2: 1 Decimal Point = '> x' becomes x + 0.1 ○ Example 3: 0 Decimal Points = '< x' becomes x - 1

10.7. Appendix 7: Reporting Standards for Missing Data

10.7.1. Premature Withdrawals

Element	Reporting Detail
General	
 • Subject study completion (i.e. as specified in the protocol) was defined as who has completed all phases of the study including the follow-up visit(s). • Withdrawn subjects may be replaced in the study. • All available data from participants who were withdrawn from the study will be listed and all available planned data will be included in summary tables and figures, unless otherwise specified.

10.7.2. Handling of Missing Data

Element	Reporting Detail
General	
 • Missing data occurs when any requested data is not provided, leading to blank fields on the collection instrument: 
 ○ These data will be indicated by the use of a “blank” in subject listing displays. Unless all data for a specific visit are missing in which case the data is excluded from the table. ○ Answers such as “Not applicable” and “Not evaluable” are not considered to be missing data and should be displayed as such.
Outliers	
 • Any participants excluded from the summaries and/or statistical analyses will be documented along with the reason for exclusion in the clinical study report.

10.7.2.1. Handling of Missing and Partial Dates

Element	Reporting Detail
General	
 • Partial dates will be displayed as captured in subject listing displays.
Adverse Events	
 • The eCRF does not allow for the possibility of partial dates. The eCRF and the site need to enter the full date or if not known, they would be required to complete an item level comment bubble to specify why the date is unknown. This would also be documented in the Data Quality Release Report by DM. • Completely missing start or end dates will remain missing, with no imputation applied. Consequently, time to onset and duration of such events will be missing
Concomitant Medications/Medical History	
 • Partial dates for any concomitant medications recorded in the CRF will be imputed using the following convention: 
 ○ If the partial date is a start date, a '01' will be used for the day and 'Jan' will be used for the month ○ If the partial date is a stop date, a '28/29/30/31' will be used for the day (dependent on the month and year) and 'Dec' will be used for the month. • The recorded partial date will be displayed in listings.

10.8. Appendix 8: Values of Potential Clinical Importance

10.8.1. Laboratory Values

Haematology				
Laboratory Parameter	Units	Category	Clinical Concern Range	
			Low Flag (< x)	High Flag (>x)
Hematocrit	Ratio of 1			
		Female	0.3	0.54
		Δ from BL		
Haemoglobin	g/L			
		Female	80	180
		Δ from BL		
Lymphocytes	x10 ⁹ /L		0.8	
Neutrophil Count	x10 ⁹ /L		1.5	
Platelet Count	x10 ⁹ /L		100	550
White Blood Cell Count (WBC)	x10 ⁹ /L		3	22

Liver Function			
Test Analyte	Units	Category	Clinical Concern Range
ALT/SGPT	U/L	High	≥ 3x ULN
AST/SGOT	U/L	High	≥ 3x ULN
AlkPhos	U/L	High	≥ 3x ULN
T Bilirubin	μmol/L	High	≥ 1.5xULN
T. Bilirubin + ALT	μmol/L U/L	High	1.5xULN T. Bilirubin + ≥ 2x ULN ALT

10.8.2. Vital Signs

Vital Sign Parameter (Absolute)	Units	Clinical Concern Range	
		Lower	Upper
Systolic Blood Pressure	mmHg	< 85	> 160
Diastolic Blood Pressure	mmHg	< 45	> 100
Heart Rate	bpm	< 40	> 110

10.9. Appendix 9: Abbreviations & Trade Marks

10.9.1. Abbreviations

Abbreviation	Description
AE	Adverse Event
AIC	Akaike's Information Criteria
A&R	Analysis and Reporting
CI	Confidence Interval
CPMS	Clinical Pharmacology Modelling & Simulation
COC	Combined Oral Contraceptive
non-COC	non-Combined Oral Contraceptive
CPSSO	Clinical Pharmacology Science & Study Operations
CS	Clinical Statistics
CSR	Clinical Study Report
CTR	Clinical Trial Register
CV _b / CV _w	Coefficient of Variation (Between) / Coefficient of Variation (Within)
DBF	Database Freeze
DBR	Database Release
DOB	Date of Birth
DP	Decimal Places
eCRF	Electronic Case Record Form
ECG	Electrocardiogram
EMA	European Medicines Agency
F	Inhaled Bioavailability
FDA	Food and Drug Administration
FDAAA	Food and Drug Administration Clinical Results Disclosure Requirements
FEV1.0	Forced expiratory volume at 1 minute
FPD	Future Pipelines Discovery
GSK	GlaxoSmithKline
IA	Interim Analysis
ICH	International Conference on Harmonization
IDMC	Independent Data Monitoring Committee
IDSL	Integrated Data Standards Library
IH	Inhaled
IM	Intramuscular
IMMS	International Modules Management System
IP	Investigational Product
I.U.	International units
IV	Intravenous
MMRM	Mixed Model Repeated Measures
PCI	Potential Clinical Importance
PCPS	Projects, Clinical Platforms and Sciences
PD	Pharmacodynamic
PDMP	Protocol Deviation Management Plan
PK	Pharmacokinetic

Abbreviation	Description
PP	Per Protocol
PopPK	Population PK
QC	Quality Control
QTcF	Frederica's QT Interval Corrected for Heart Rate
QTcB	Bazett's QT Interval Corrected for Heart Rate
RAP	Reporting & Analysis Plan
SAC	Statistical Analysis Complete
SAE	Serious Adverse Event
SPDS	Statistics, Programming and Data Sciences
SOP	Standard Operation Procedure
TA	Therapeutic Area
TFL	Tables, Figures & Listings
TSL	Third stage of labour

10.9.2. Trademarks

Trademarks of the GlaxoSmithKline Group of Companies
ROTAHALER

Trademarks not owned by the GlaxoSmithKline Group of Companies
WinNonlin

10.10. Appendix 10: List of Data Displays

10.10.1. Data Display Numbering

All displays (Tables, Figures & Listings) will use the term 'Subjects'. The following numbering will be applied for RAP generated displays:

Section	Tables	Figures
Study Population	1.7-1.12	N/A
Pharmacokinetic	2.6-2.8	2.8
Safety	3.17-3.28	3.1
Section	Listings	
ICH Listings	35-50	
Other Listings	51-53	

10.10.2. Mock Example Shell Referencing

Non IDSL specifications will be referenced as indicated and if required example mock-up displays provided in [Appendix 11: Example Mock Shells for Data Displays](#).

Section	Figure	Table	Listing
Safety	SAFE_FN	SAFE_TN	SAFE_LN
Pharmacokinetic	N/A	PK_TN	NA

NOTES:

- Non-Standard displays are indicated in the 'IDSL / Example Shell' or 'Programming Notes' column as '[Non-Standard] + Reference.'

10.10.3. Deliverables

Delivery [Priority] ^[1]	Description
DR [1]	Prior to DBR. Dry Run for Study Pop, Safety displays
SAC	Final Statistical Analysis Complete

NOTES:

1. Indicates priority (i.e. order) in which displays will be generated for the reporting effort

10.10.4. Study Population Tables

Study Population Tables					
No.	Population	IDSL / Example Shell	Title	Programming Notes	Deliverable [Priority]
Subject Disposition					
1.7.	Safety	ES1	Summary of Subject Disposition for the Subject Conclusion Record	ICH E3, FDAAA, EudraCT	DR [1], SAC
1.8.	Enrolled	NS1	Summary of Number of Subjects Enrolled by Country and Site ID	EudraCT/Clinical Operations	DR [1], SAC
Population Analysed					
1.9.	Screened	SP1	Summary of Study Populations		DR [1], SAC
Demographic and Baseline Characteristics					
1.10.	Safety	DM1	Summary of Demographic Characteristics	ICH E3, FDAAA, EudraCT	DR [1], SAC
1.11.	Enrolled	DM11	Summary of Age Ranges	EudraCT	DR [1], SAC
1.12.	Safety	DM5	Summary of Race and Racial Combinations	ICH E3, FDA, FDAAA, EudraCT	DR [1], SAC

10.10.5. Pharmacokinetic Tables

Pharmacokinetic Tables					
No.	Population	IDSL / Example Shell	Title	Programming Notes	Deliverable [Priority]
PK Concentration Data					
2.6.	PK	pkct1	Summary of Plasma Concentration-time Data	Page by subjects before study restart, subjects after restart and all subjects together.	SAC
2.7.	PK	PK_T1	Summary of Derived Plasma Pharmacokinetic Parameters (untransformed data)	Page by subjects before study restart, subjects after restart and all subjects together. This will be an overall summary and will not be displayed by timepoints.	SAC
2.8.	PK	PK_T2	Summary of Number and Percentage of Subjects with Measurable Concentrations	Page by subjects before study restart, subjects after restart and all subjects together. This will be an overall summary and will not be displayed by timepoints.	SAC

10.10.6. Pharmacokinetic Figures

Pharmacokinetic Figures					
No.	Population	IDSL / Example Shell	Title	Programming Notes	Deliverable [Priority]
Individual Concentration Plots					
2.8.	PK	pkcf6	Individual Subject Plasma Concentration-time Plot (Linear and Semi-log) by Treatment	By Treatment, Page by subjects before study restart, subjects after restart and all subjects together	SAC

10.10.7. Safety Tables

Safety: Tables					
No.	Population	IDSL / Example Shell	Title	Programming Notes	Deliverable [Priority]
Adverse Events (AEs)					
3.17.	Safety	AE1	Summary of All Adverse Events by System Organ Class and Preferred Term		DR [1], SAC
3.18.	Safety	AE1	Summary of Drug-Related Adverse Events		DR [1], SAC
3.19.	Safety	AE1	Summary of Non-Serious Adverse Events		DR [1], SAC
3.20.	Safety	AE15	Summary of Common (>1 Subject) Non-serious Adverse Events by System Organ Class and Preferred Term (Number of Subjects and Occurrences)	FDAAA, EudraCT	DR [1], SAC
Serious and Other Significant Adverse Events					
3.21.	Safety	AE16	Summary of Serious Adverse Events by System Organ Class and Preferred Term (Number of Subjects and Occurrences)	FDAAA, EudraCT	DR [1], SAC
3.22.	Safety	AE1	Summary of Adverse Events Leading to Permanent Discontinuation of Study Drug or Withdrawal from Study		DR [1], SAC

Safety: Tables					
No.	Population	IDSL / Example Shell	Title	Programming Notes	Deliverable [Priority]
Laboratory: Hematology					
3.23.	Safety	LB1	Summary of Haematology Values		DR [1], SAC
3.24.	Safety	LB1	Summary of Haematology Changes from Baseline		DR [1], SAC
Vital Signs					
3.25.	Safety	VS1	Summary of Vital Signs		DR [1], SAC
3.26.	Safety	VS1	Summary of Change from Baseline for Vital Signs		DR [1], SAC
3.27.	Safety	VS7	Summary of Vital Sign Results Relative to Potential Clinical Importance (PCI) Criteria Post-Baseline Relative to Baseline		DR [1], SAC
Exploratory : Questionnaire Results					
3.28.	Safety	SAFE_T1	Summary of Device Acceptability Questionnaire for Rotahaler Inhaler		DR[1], SAC

10.10.8. Safety Figure

Safety: Figures					
No.	Population	IDSL / Example Shell	Title	Programming Notes	Deliverable [Priority]
Adverse Events					
3.1.	Safety	LB10	Safety Summary Plot of Pre and Post-Delivery Haemaglobin	IDSL Include the timepoints in the x-axis and values in the y-axis	DR[1], SAC

10.10.9. ICH Listings

ICH: Listings					
No.	Population	IDSL / Example Shell	Title	Programming Notes	Deliverable [Priority]
Subject Disposition					
35	Screened	ES7	Listing of Reasons for Screening Failure		DR [1], SAC
36.	Safety	ES2	Listing of Reasons for Withdrawal		DR [1], SAC
37.	Safety	TA1	Listing of Randomised and Actual Treatments		DR [1], SAC
Protocol Deviations					
38.	Safety	DV2	Listing of Important Protocol Deviations		DR [1], SAC
39.	Safety	IE3	Listing of Participants with Inclusion/Exclusion Criteria Deviations		DR [1], SAC
Populations Analysed					
40.	Enrolled	SP3	Listing of Participants Excluded from Analysis Population		DR [1], SAC
Demographic and Baseline Characteristics					
41.	Safety	DM2	Listing of Demographic Characteristics		DR [1], SAC
42.	Safety	DM9	Listing of Race		DR [1], SAC
Prior and Concomitant Medications					
43.	Safety	CM3	Listing of Concomitant Medications		DR [1], SAC
Exposure and Treatment Compliance					
44.	Safety	EX3	Listing of Exposure Data		DR [1], SAC
Adverse Events					
45.	Safety	AE8	Listing of All Adverse Events		DR [1], SAC
46.	Safety	AE7	Listing of Subject Numbers for Individual Adverse Events		DR [1], SAC

ICH: Listings					
No.	Population	IDSL / Example Shell	Title	Programming Notes	Deliverable [Priority]
Serious and Other Significant Adverse Events					
47.	Safety	AE8	Listing of Serious Adverse Events		DR [1], SAC
48.	Safety	AE8	Listing of Adverse Events Leading to Withdrawal from Study		DR [1], SAC
All Laboratory					
49.	Safety	LB5	Listing of All Hematology Data	All PCI criteria will be flagged	DR [1], SAC
Vital Signs					
50.	Safety	VS4	Listing of All Vital Signs Data	All PCI criteria will be flagged	DR [1], SAC

10.10.10. Non-ICH Listings

Non-ICH: Listings					
No.	Population	IDSL / Example Shell	Title	Programming Notes	Deliverable [Priority]
Safety					
51.	Safety	SAFE_L1	Listing of Device Acceptability Questionnaire for Rotahaler Inhaler		DR [1], SAC
PK Concentration					
52.	PK	PK07	Listing of Plasma Pharmacokinetic Concentration-Time Data		SAC
53.	PK	PK13	Listing of Derived Plasma Pharmacokinetic Parameters		SAC

10.11. Appendix 11: Mock Shell

Example: SAFE_T1
Protocol: 205920
Population: Safety

Table x.xx
Summary of Device Acceptability Questionnaire for Rotahaler Inhaler

	Total (N=XX)

Feel Confident Received the Medicine	
n	xx
Yes	xx (xx%)
No	xx (xx%)
Neutral	xx (xx%)
Decline to Answer	xx (xx%)
Find This Inhaler Easy to Use	
n	xx
Yes	xx (xx%)
No	xx (xx%)
Neutral	xx (xx%)
Decline to Answer	xx (xx%)
Prefer Inhaler Instead of Injection	
n	xx
Yes	xx (xx%)
No	xx (xx%)
Neutral	xx (xx%)
Decline to Answer	xx (xx%)

Example: SAFE_T1
Protocol: 205920
Population: Safety

Table x.xx
Summary of Device Acceptability Questionnaire for Rotahaler Inhaler

	Total (N=XX)

This Inhaler Acceptable to Administer	
n	xx
Yes	xx (xx%)
No	xx (xx%)
Neutral	xx (xx%)
Decline to Answer	xx (xx%)

Example : SAFE_L1
Protocol : GR121619
Population : Safety

Page 1 of n

Listing SAFE_T1
Listing of Device Acceptability Questionnaire for Rotahaler Inhaler

Site Id./ Subj Id.	Visit	Date	Question	Response
Xxxx/PPD	PERIOD 1 GRP1	PPD	Feel Confident Received the Medicine	Yes
			Find This Inhaler Easy to Use	Yes
			Prefer Inhaler Instead of Injection	Yes
			This Inhaler Acceptable to Administer	Yes
Xxxx/PPD	PERIOD 1 GRP1	PPD	Feel Confident Received the Medicine	Neutral
			Find This Inhaler Easy to Use	Yes
			Prefer Inhaler Instead of Injection	Yes
			This Inhaler Acceptable to Administer	Yes

Example: PK_T1
Population: Pharmacokinetic {Group}

Table x.x
Summary of Derived [Analyte] [Matrix] Pharmacokinetic Parameters {by Group}

Parameter	Treatment	N	n	n*	Median	Range
AUC(0-t) (units)	400mcg	24	24 24	xxxx.xx xxxx.xx	NC xxxx.xx	NC to NC NC to xx
	17mg	24	24 23	xxxx.xx xxxx.xx	xxxx.xx xxxx.xx	xxxx.x xxxx.x
Cmax (units)	400mcg	24	24 23	xxxx.xx xxxx.xx	xxxx.xx xxxx.xx	xxxx.x xxxx.x
	17mg	24	24 21	xxxx.xx xxxx.xx	xxxx.xx xxxx.xx	xxxx.x xxxx.x

NC = non calculable due to NQ concentrations

NA = not applicable due to insufficient data to derive summary measure

n = Number of subjects with non-missing observations (including imputed NC values)

n* = Number of subjects for whom parameter cannot be derived because of NQ concentrations

Note: for Cmax and AUC, NCs were imputed prior to derivation of summary statistics; No NC values were imputed for tmax.

Cmax imputed with ½ LLQ (5 pg/mL)

AUC(0-t) imputed with ½ lowest observed AUC(0-t) (5.45 pg.h/mL)

Example: PK_T2
Population: Pharmacokinetic

Table x.x
Summary of Number and Percentage of Subjects with Measurable Concentrations

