2.4. Statistical Hypotheses / Statistical Analyses

No formal hypotheses will be tested.

For IH and IM oxytocin, summary statistics will be produced separately for IH Oxytocin and IM Oxytocin. Due to sparse PK concentrations, it is not possible to include a formal statistical analysis to compare IH and IM Oxytocin. PK parameters will be derived as data permit. Individual plots, listings and summary tables will be produced for available PK concentration data. Only listings and summary tables will be produced for PK Parameter data.

3. PLANNED ANALYSES: GROUP 1

3.1. Interim Analyses: Group 1

No formal Interim Analysis are planned, however, PK samples will be analysed and preliminary PK parameters derived following completion of approximately 5 women on each treatment group: 400 mcg IH and 10 I.U. IM to women in TSL (Group 1) and 400 mcg IH to non-pregnant women on the combined oral contraceptive (Group 2 Cohort A), in order to assess if dose escalation is required.

Due to sparse PK concentration-time data available following administration of IH and IM oxytocin to women in TSL, only concentration time plots were presented at the interim analysis. The Study has been terminated early due the unanticipated inability to be able to quantify plasma oxytocin using a selective and sensitive (LLQ 2pg/mL) analytical assay due to low oxytocin concentrations (<2pg/mL) in the majority of samples collected from women in Third Stage Labour (TSL), following either IM or IH administration. Therefore, the Primary objective of the study to characterise the PK of single doses of IH and IM oxytocin in women in TSL, cannot be met, and the study is being terminated

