IH/IM	AUC(0-t)	Area under the concentration-time curve from time zero to the time of the last quantifiable concentration (C(t)) will be calculated using the linear trapezoidal rule for each incremental trapezoid and the log trapezoidal rule for each decremental trapezoid.
IH/IM	t _{last}	Time of last quantifiable concentration

At least 2 quantifiable (3 including time 0 where NQ values at time zero will be set to 0) values per profile are required to calculate the AUC(0-t). For profiles with less than 2 quantifiable values, AUC(0-t) will be coded with NC in the PKPar file.

8.1.2. Summary Measure: Group 1

Pharmacokinetic concentration data will be presented in graphical and/or tabular form and will be summarized descriptively by IH oxytocin and IM Oxytocin.

The conversion factor to normalise IM doses is 1 IU = 1.7 mcg oxytocin

As a large number of PK parameter values will be reported as Non Calculable (NC: PK parameter cannot be derived due to the presence of non-quantifiable data) then the PK parameter will be summarised by following measures

- number of subjects with non-missing observations, n, (includes those reported as NC)
- number of subjects for whom parameter cannot be derived because of NQ concentrations, n*, (reported as NC)
- median, minimum and maximum

In addition a frequency table of the number of subjects with all concentrations NQ and the number of subjects with one, or 2 or more measurable concentrations will be produced.

8.1.3. Population of Interest : Group 1

The primary pharmacokinetic analyses will be based on the Pharmacokinetic population, unless otherwise specified.

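### Group 1 shell PK_T1 imputes a non-calculable Cmax at 5 pg/mL and calls it half the LLQ, but half of the only stated LLQ (2 pg/mL) is 1 pg/mL

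*SAP*

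**What the plan says.** All references are to the Group 1 RAP unless noted.

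- **Assay limit.** Section 3.1 explains the early termination by the inability to quantify oxytocin "using a selective and sensitive (LLQ 2pg/mL) analytical assay", with "low oxytocin concentrations (<2pg/mL) in the majority of samples collected from women in Third Stage Labour (TSL". No other LLQ appears anywhere in the document.
- **Summary rule.** Section 8.1.2 opens its rule with "As a large number of PK parameter values will be reported as Non Calculable" and then asks for n, n*, median, minimum and maximum. It gives no imputation value. Section 10.5.2 refers the PK parameter table back to 8.1.2.
- **AUC.** Section 8.1.1.2 says: "For profiles with less than 2 quantifiable values, AUC(0-t) will be coded with NC in the PKPar file".
- **Shell PK_T1 (Appendix 11).** The footnotes say that "for Cmax and AUC, NCs were imputed prior to derivation of summary statistics". They then give the two fill-in values: "Cmax imputed with ½ LLQ (5 pg/mL" and "AUC(0-t) imputed with ½ lowest observed AUC(0-t) (5.45 pg.h/mL".
- **Where the shell is used.** Appendix 10 assigns PK_T1 to Table 2.7, the only Group 1 summary table of the derived PK parameters. It is paged by women before the study restart, women after it, and all women.
- **Dose label.** PK_T1 labels the IM arm 17mg; Section 5.1 labels it 17 mcg.

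**The concern.** The fill-in is described as half the LLQ, yet its value exceeds the LLQ. A substitute for values too low to measure has to lie below every measured value, or the ordering on which a median and range depend is broken. With 5 pg/mL, an unmeasurable Cmax outranks a measured Cmax of 2 to 5 pg/mL.

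The footnote is the only written Group 1 fill-in for an NC Cmax. The Group 2 RAP cites a standard for parameters affected by non-quantifiable (NQ) values in its Section 10.5.3; the Group 1 counterpart has no such entry. A programmer who follows the shell therefore has nothing to correct it against. What is at stake is the median and range of Cmax, a primary endpoint, in the only table that summarises it.

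**Working it through.** **Inputs.** LLQ 2 pg/mL (Section 3.1); fill-in 5 pg/mL (PK_T1 footnote); imputation before the summary statistics (PK_T1 footnote); median, minimum and maximum as summary (Section 8.1.2).

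**Step 1: try to reproduce the printed figure.**

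- Half the LLQ: 0.5 × 2 = 1 pg/mL.
- The LLQ itself: 2 pg/mL. Zero, the Section 10.5.2 rule for NQ concentrations: 0.
- None gives 5. The printed figure needs an LLQ of 5 × 2 = 10 pg/mL, which is stated nowhere.
- Size of the discrepancy: 5 / 1 = 5 times half the LLQ, and 5 / 2 = 2.5 times the LLQ.

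**Step 2: effect on the median.** The RAP does not say how many women have an NC Cmax, so the share is varied. Assumptions: 24 women in an arm (the shell's placeholder N), of whom k are NC. The measured Cmax values are evenly spaced over either 2.1–4.9 or 2.1–20 pg/mL. Each cell gives the median with fill-in 5 against fill-in 1.

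| NC women (k of 24) | Measured 2.1–4.9 | Measured 2.1–20 |
|---|---|---|
| 6 | 3.99 vs 3.01 (ratio 1.33) | 7.89 vs 7.89 (1.0) |
| 11 | 4.78 vs 2.22 (2.15) | 5.0 vs 2.85 (1.75) |
| 12 | 4.95 vs 1.55 (3.19) | 5.0 vs 1.55 (3.23) |
| 13 or more | 5 vs 1 (5.0) | 5 vs 1 (5.0) |

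Once more than half the arm is NC, the ratio is exactly 5 whatever the measured values are.

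**Step 3: effect on the range.** With the correct fill-in, the minimum is 1 pg/mL whenever any woman is NC. With 5 it is the smaller of 5 and the lowest measured value: 2.1 in the mixed sets above, and 5 if every woman is NC. The maximum can move too: with measured values of 2.1–4.9 and any NC woman it becomes 5 instead of 4.9, or 5 instead of 1 if all are NC.

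**Step 4: the AUC constant.** 5.45 × 2 = 10.9 pg.h/mL would be the lowest observed AUC(0-t). The RAP reports no observed AUC, so this cannot be checked. The written rule itself, half the lowest observed value, always lies below every observed AUC.

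**Step 5: the dose label.** Section 8.1.2 converts 1 IU to 1.7 mcg; 10 × 1.7 = 17 mcg. The shell prints the same digits in milligrams, a thousandfold difference in unit.

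**The case against.** The strongest defence is that PK_T1 is headed as an example and carries placeholders for analyte, matrix, units, N and most cells. The 5 and 5.45 may simply have come with a template. That is plausible but cannot be shown, and it does not rescue the footnote: both figures carry units, and no other Group 1 text supplies the correct value. It does weaken any claim that 5.45 is a constant deliberately fixed before the final analysis.

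The consequences are also bounded. Section 3.1 already says that the primary objective cannot be met, and no hypothesis is tested. The n* column, Table 2.8, Figure 2.8 and Listings 52 and 53 would show the NQ burden and the individual data, so an attentive reader could notice an odd median. This limits the harm but leaves Table 2.7 wrong.

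A reader might infer three stronger points that the document does not support:

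- *That the median will be five times too high.* Section 3.1 counts samples, not women. Appendix 2 schedules 12 PK samples per woman, and one quantifiable sample is enough for a Cmax. Most samples can be NQ while fewer than half the women are NC.
- *That the shell contradicts Section 8.1.2.* That section is silent on imputation; it neither forbids it nor says that a median falling on an NC is to be printed as NC.
- *That the shell contradicts itself because its first AUC row shows NC entries beside an imputation footnote.* The extracted table is broken. That row may depict an arm in which every AUC is NC, so that no observed AUC was available there to halve.

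**Conclusion.** The error stands and should be corrected before Table 2.7 is produced. Given the 2 pg/mL LLQ, the Cmax fill-in should be 1 pg/mL; the printed 5 pg/mL is five times that and lies above the LLQ.

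The effect on the median is conditional: 5 instead of 1 pg/mL if more than half of an arm is NC, and a ratio between 1.0 and about 3.2 in the illustrative sets with half or fewer NC. The minimum is wrong whenever at least one woman is NC. These results assume that the 2 pg/mL limit applies to all Group 1 samples and that the footnote is followed literally; the arm size and measured values in the illustration are assumptions. The AUC rule is sound as worded; only its printed number needs attention. The IM label is a separate inconsistency with no bearing on this arithmetic.

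**What to change.** 1. In the PK_T1 footnote, print half the LLQ as 1 pg/mL. If the assay differed before and after the restart, state the LLQ and the resulting fill-in for each period, since Table 2.7 is paged that way.
2. Replace 5.45 pg.h/mL with a blank field, to be filled as half the lowest AUC(0-t) observed in the final Group 1 data.
3. Move the imputation rule into Section 8.1.2, and say there what is displayed when all values are NC.
4. Separately, reconcile the IM dose label in PK_T1 with Section 5.1.

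The cost is two footnotes, one constant in the program, a few sentences in 8.1.2 and a label check. No data collection or other analysis changes.
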